## ORAL HEALTH EDUCATION SENIORS

completing baseline and follow up assessments during the calibration exercise that may require an estimated 3 hours during a 1 month period. These follow up sessions will be scheduled based on the patients and the hygienist's availability. The calibration group will also sign a HIPAA Authorization form. Please see Appendix D.

### **Data Management:**

All demographic information and questionnaires will be administered in person. Data will be entered into an excel spreadsheet. Data will be downloaded to an IBM-compatible computer and stored on a password-protected account, and it will be exported to a computer data analysis program (SAS/SPSS). Data will be cleaned and checked for errors prior to the analysis; imputation procedures for handling missing data will be conducted depending on the number of cases with missing data. Participant names and corresponding identification numbers will be stored separately in a locked file cabinet or password-protected file.

### **Data Analysis:**

Initial analyses will be conducted to determine normality of distributions of the continuous variables, and any necessary transformations will be conducted. Primary outcomes will be the OHIP 14 and the self-efficacy scores. All eligible patients will be randomly assigned to 1 of the 3 groups described above. Although randomization should provide relatively comparable groups, demographic variables that differ between groups and are correlated with the primary outcomes will be used as covariates. Preliminary analysis will include measures of central tendency and dispersion, as well as an examination of the bivariate relationships among the primary and secondary outcome variables, potential moderators, and demographic characteristics.

Differences between the groups on baseline demographic, and psychological measures will be examined using  $\chi^2$  (Pearson) or Student's *t*-tests, as appropriate. Moreover, differences on the variables listed above among completers and drop-outs will also be explored. Intention to treat (ITT) analyses will then be conducted.

OHIP 14 and self-efficacy scores will be the primary outcomes. Initially, we will assess the differences between the interventions and control using 2-sample *t*-tests. The main analysis will be based on linear mixed-effects models for repeated measures (using the OHIP 14 and self-efficacy scores as continuous outcome variables) to assess differences between intervention and control groups. Similar analyses will be conducted for secondary outcome measures. Statistical significance will be set at  $p < .05$ .

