### **4) Objectives**

- **Primary Objective:**

The objective of this study is to test the efficacy of an oral health education group based activity versus an individual oral health education activity in terms of changes in oral health related quality of life (OHRQoL), self-efficacy and oral health knowledge.

- **Secondary Objective**

The secondary objective of this study is:

a) To assess differences among intervention and control groups by senior's oral health knowledge.

- **Overall Hypotheses**

Ho: There are no significant differences in the selected behavioral outcome measures between the interventions, either group-based or individual based education and the control.

Ho: The two educational interventions are not equivalent in the selected behavioral outcome measures.

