### **Control Group: (60 seniors).**

Seniors who are randomly assigned to the control group will continue receiving regular dental care under the standard clinic operation. Subjects in this group will complete intake forms to assess main behavioral outcomes, at baseline and after 12 months. No other activities will be conducted in this group.

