### **Intervention Group 1: (60 seniors).**

Seniors who are randomly assigned to the intervention group 1 will continue receiving regular dental care under the standard clinic operation and will be invited to participate in 2 group based education activities over a 12 month period. The sessions will last for 1 hour each time and follow the guidelines established by the Oral Health America Curriculum. Baseline intake forms to assess changes in main behavioral outcomes will be administered before the first education session, after 6 months and after 12 months.

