### **Intervention Group 2: (70 seniors (10 of these are calibration patients exclusively)).**

Seniors who are randomly assigned to the intervention group 2 will continue receiving regular dental care under the standard clinic operation and will also be invited to participate in an individual-based education activity over a 12 month period. The clinic visits will last for 1 hour each time and follow the guidelines established by TUKSoD to provide oral hygiene instruction using a Motivational Interviewing approach. Tailored education will be based on review of health related information to be extracted from medical (systemic diseases), dental chart (oral hygiene behaviors) and patient interview at time of initial examination. Seniors in this group will also receive basic preventative care (dental cleanings, fluoride varnish application (high caries risk individuals only) or referral to a supervised brushing program with high concentration fluoride under the care of the dentist at Kleinlife if needed. All individual based preventative activities will be provided by a Public Health Hygienist, and 3 dental visits will be conducted for subjects in this group during the course of a 18 month period. Baseline intake forms to assess changes in main behavioral outcomes will be administered before the first home based education session, at each follow up visit and after 18 months.

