## ORAL HEALTH EDUCATION SENIORS

study:

- Oral Health Related Quality of Life: The Short-Form Oral Health Impact Profile (OHIP-14; Slade, 1997) is a 14-item self-report measure that assesses individuals' perceptions of the social impact of oral conditions on their well-being. This scale evaluates the consequences of oral conditions across dimensions of functional limitation, physical pain, psychological discomfort, physical disability, psychological disability, social disability, and handicap. Items are rated on a 5-point Likert-type scale ranging from 0 (*never*) to 4 (*very often*), regarding how frequently impact has been experienced. The total score ranges from 0 to 56; higher OHIP-14 scores indicate greater impact, hence poorer oral-health-related quality of life. The OHIP-14 has been validated in two national surveys of populations in the UK and Australia (Kelly et al., 1998; Steele et al., 2004) and demonstrated good reliability, construct and discriminant validity, and internal consistency (Slade & Spencer, 1994; Slade, 1997).
- Self-efficacy will be assessed based on a modified version of an instrument developed by Finlayson and colleagues (Finlayson et al, 2007). It will be measured using a 6-item scale, asking participants to indicate how confident they feel about their ability to brush their teeth at night when they were: (1) under a lot of stress; (2) depressed; (3) anxious; (4) feeling that they were too busy; (5) tired or; (6) worried about other things in their life. The four response options range from 'very confident' to 'not at all confident'. The possible score range is 0 to 24, with high scores indicating high self-efficacy. Alpha was 0.91. Self-efficacy will be dichotomized based on a median split, with low self-efficacy pertaining to scores of 0 to 11 and high self-efficacy pertaining to scores of 12+.
- Oral Health Knowledge: A 15-item questionnaire with a three-point Likert Scale (yes, no, and don't know) will be used to assess the oral health information/knowledge of the seniors pre and post intervention. Its respective psychometric properties (validity and reliability) have already been reported (Khanagar et al, 2014).
- Demographic Factors Questionnaire will identify key demographic factors such as age, sex, race, ethnicity, education and income level of seniors.

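### Covariates are selected from the trial's own data, while the baseline OHIP-14 and self-efficacy scores have no stated role in the main model

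*Combined protocol and SAP*

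**What the plan says.** All the analysis text is in the Data Analysis section under Study Procedures and Data Analysis of the combined protocol and SAP.

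- **Outcomes:** "OHIP 14 and self-efficacy scores will be the primary outcomes", both treated as continuous.
- **Model:** "The main analysis will be based on linear mixed-effects models for repeated measures". No fixed effects, time coding, group-by-time term or contrast time is listed.
- **Covariates:** "demographic variables that differ between groups and are correlated with the primary outcomes will be used as covariates". No test or threshold is given for either condition. Nor does the text say which of the three arm comparisons, or which of the two primary outcomes, decides.
- **Baseline scores:** baseline demographic and psychological measures are to be compared between groups, but only demographics are named as possible covariates.

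Elsewhere in the document:

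- **Objectives** frames the aim "in terms of changes in oral health related quality of life (OHRQoL), self-efficacy and oral health knowledge".
- **Control Group:** "Subjects in this group will complete intake forms to assess main behavioral outcomes, at baseline and after 12 months".
- **Intervention Group 1:** "Baseline intake forms to assess changes in main behavioral outcomes will be administered before the first education session", then at 6 and 12 months.
- **Intervention Group 2:** the forms "will be administered before the first home based education session, at each follow up visit and after 18 months".
- **Measurements:** "Demographic Factors Questionnaire will identify key demographic factors such as age, sex, race, ethnicity, education and income level of seniors".

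The baseline scores and the demographics are therefore already collected in every arm.

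**The concern.** In a randomized trial, a covariate is worth including for how well it predicts the outcome, and it should be named beforehand. The plan instead lets chance imbalance decide and considers only demographics. The variable most likely to predict a follow-up questionnaire score is the same score at baseline, and that has no defined role.

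The model named in the plan can be fitted in several ways that differ in precision: baseline as a covariate; baseline as a response with one mean common to all arms; baseline as a response with a free mean in each arm (in effect a change-score contrast); or no use of baseline at all. Two analysts following the text could report different standard errors for the same primary comparison. The protocol gives no power calculation for its 60 per arm, so there is no documented margin to absorb an inefficient choice.

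**Working it through.** **Inputs from the documents.** Arm sizes are 60, 60 and 70, which sum to the stated 190. Ten of the 70 are calibration patients only, leaving 60 per arm. Significance is set at 0.05; two-sided is assumed.

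**Assumptions, because the documents give no figure.** True difference d = 0.5 SD; correlation r between baseline and follow-up scores of 0.3, 0.5, 0.7 or 0.8; no dropout; equal variances; one follow-up score. There is no stated power to reproduce.

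**Formula.** In SD units the variance of the between-arm contrast is k × 2/n, where

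- k = 1 for follow-up scores only,
- k = 2(1 − r) with a free baseline mean in each arm,
- k = 1 − r² with baseline as a covariate or a common baseline mean.

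Power comes from the noncentral t distribution with 118 df and noncentrality d / √(k × 2/60).

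**Example, r = 0.3.** Free means: k = 1.40, noncentrality 0.5/√(1.40/30) = 2.315, power 63.1%. Baseline-adjusted: k = 0.91, noncentrality 0.5/√(0.91/30) = 2.871, power 81.3%. The gain is about 18 points.

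| r | Follow-up only | Free means | Baseline-adjusted | Gain over free means | Gain over follow-up only |
|---|---|---|---|---|---|
| 0.3 | 77.5% | 63.1% | 81.3% | 18.1 | 3.7 |
| 0.5 | 77.5% | 77.5% | 88.0% | 10.5 | 10.5 |
| 0.7 | 77.5% | 93.9% | 96.7% | 2.8 | 19.2 |
| 0.8 | 77.5% | 99.0% | 99.5% | 0.5 | 22.0 |

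(Gains are in power points, from unrounded powers.)

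Against free means the variance ratio is (1 − r²)/[2(1 − r)] = (1 + r)/2, a reduction of 35/25/15/10%. The free-mean model would need 60 × 2/(1 + r) = 92/80/71/67 per arm to match 60 with adjustment. Against follow-up only the reduction is r² = 9/25/49/64%.

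**Sensitivity.** The gain over free means is 17.4/12.4/6.0/2.2 points at d = 0.4 and 14.1/6.1/0.8/0.0 at d = 0.6. At r = 0.3 it is about 6 points for d = 0.2 and 4 for d = 0.8. At d = 0.5 and r = 0 it is 29 points, where the gain over follow-up only is zero.

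**The covariate screen.** This was simulated with 10,000 three-arm trials per setting and six continuous demographics. Each had an assumed correlation of 0.1 or 0.2 with the outcome and was selected when p < .05 for both imbalance and correlation. At least one covariate was selected in 6–17% of trials for one pair of arms. Type I error was 4.3–5.2% with the screen and 4.8–5.4% without. Power on follow-up scores was 76.7–77.4% with and 77.3–77.7% without, with a largest difference of 0.6 points. A separate two-arm simulation of 8,000 runs, with correlations of 0.2 to 0.5, gave type I error of 3.8–4.8%, slightly conservative.

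**The case against.** The strongest reply is that the quoted sentence does almost no damage. That stands: the power figures above measure how baseline is handled, not the screen. A reader might infer that choosing covariates from the data inflates type I error; neither simulation showed this. Those simulations are only illustrative, because they used continuous covariates and assumed thresholds, whereas the demographic form in Appendix C records all but age and ZIP code as categories.

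A second reply is that a repeated-measures model may already use baseline well. That also stands in part. If baseline was meant as a covariate, or as a response with a common mean, nothing is lost. The text does not say so.

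Two firmer readings are tempting, and the documents support neither. The first is that the control arm, having only baseline and 12 months, must have its baseline treated as a response. The intervention arms have several later assessments, so a model of post-baseline scores with baseline as a covariate can be fitted with a single record per control participant. The second is that the plan commits to a change-score analysis. The word appears in the aim and in the description of the forms, but the Data Analysis section names the scores themselves as outcomes. It leaves that reading open and no more.

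It is also fair that the calculation applies cleanly only to Intervention 1 versus control at 12 months, because the listed assessment times for Intervention 2 differ.

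**Conclusion.** The concern holds as a specific improvement available without new data, and the change should be made. The covariate rule depends on the data and adds almost no precision, and the baseline score of each primary outcome, already collected, has no defined role.

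The size is illustrative. It depends on the assumed effect, on the correlation and on which unadjusted analysis is the comparator. The two comparators move in opposite directions: the gain falls with r against free baseline means and rises with r against follow-up scores only. A reader might take 18 or 22 points as an upper limit. It is not one, as the 29 points at r = 0 against free means shows, and the lower end is zero if a common baseline mean was intended. None of these figures shows that the trial is underpowered or that its test would be invalid.

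**What to change.** Replace the covariate sentence in Data Analysis with:

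> Each outcome's mixed model adjusts for that outcome's baseline score (as a covariate, or as a response with the baseline mean constrained equal across arms). Any demographic covariates are fixed before outcome data are seen; none is selected from between-group tests.

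The SAP should keep one of the two baseline options. Candidates for the demographic list are those already in the questionnaire: age, sex, race, ethnicity, education and income. If none is named by then, none is used.

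The cost is one short paragraph of SAP wording, with no new data. The treatment contrast also needs an assessment time common to the arms compared. That requires the schedules under Control Group, Intervention Group 1 and Intervention Group 2 to be reconciled, which is a separate issue and adds nothing to the weight of this one.

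### The covariate rule and a drop-out check that ignores arm will usually leave a baseline predictor of drop-out and outcome out of the mixed model, so drop-out that differs by arm can bias the comparison

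*Combined protocol and SAP*

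**What the plan says.** All three relevant rules are in section 7d, Data Analysis.

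- **Drop-out check.** Baseline demographic and psychological measures are first compared between groups ("Differences between the groups on baseline demographic, and psychological measures will be examined using" chi-square or t-tests). The plan then adds that "differences on the variables listed above among completers and drop-outs will also be explored". Arm is not among the variables listed. No by-arm rate, profile or interaction is planned, and no use of the result is stated.
- **Covariates.** The plan says that "demographic variables that differ between groups and are correlated with the primary outcomes will be used as covariates". A variable must be demographic, differ between groups and correlate with the outcomes. Predicting drop-out does not admit it.
- **Analysis.** "Intention to treat (ITT) analyses will then be conducted". Two-sample t-tests come first, and then "The main analysis will be based on linear mixed-effects models for repeated measures". The fixed effects and the missing-data assumption are not given. Data Management allows imputation depending on how many cases are missing, without naming a method or variables.

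Follow-up differs by arm. Controls complete forms "at baseline and after 12 months. No other activities will be conducted in this group". Group 1 completes them at baseline, 6 and 12 months. Group 2 completes them before the first session, "at each follow up visit and after 18 months", although the same paragraph also gives a 12-month period for the education activity. Completer is not defined.

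**The concern.** A likelihood-based mixed model gives a valid arm contrast under drop-out only if, given the variables it contains, drop-out is unrelated to the missing values. A baseline variable that drives both drop-out and follow-up therefore needs to be in the model.

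The covariate rule asks a different question: whether the arms differ on that variable at baseline. In a randomised trial such differences arise by chance, so the rule admits a predictor of drop-out only by accident. A non-demographic predictor, such as baseline oral health knowledge, cannot enter under it at all.

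The drop-out check does not fill the gap. Bias in an arm contrast comes from drop-out that works differently by arm, and a comparison that ignores arm is not aimed at that. Different dependence by arm is possible here: the arms differ in sessions, forms and length of follow-up, and section 7e lets staff withdraw subjects for not following instructions, of which the education arms have more. The main result could then carry a bias that an already collected variable would have removed.

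**Working it through.** **Inputs from the documents.** There are 60 seniors per arm (Group 2 has 70, of whom 10 are for calibration only) and significance is set at 0.05, taken here as two-sided. The documents give no attrition rate, SD, effect size or power calculation, so there is no figure to reproduce.

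**Assumptions.** No true effect; outcome SD 1; 25% drop-out in each arm; baseline-to-follow-up correlation 0.5. A baseline variable X (SD 1) has slope b on follow-up beyond the baseline score. Drop-out follows a logistic model with log-odds slope g per SD of X, set by arm. The mixed model is represented by its two-time-point counterpart: follow-up in completers regressed on arm and baseline score.

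**Step 1: can X enter under the plan's rule?** Judged at p < 0.05, a randomised X differs between two given arms in about 5% of trials, and between at least one of the three pairs in about 12%. It usually stays out.

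**Step 2: bias when X is out.** Bias = b × (difference between arms in the mean of X among completers). At 25% drop-out that mean shifts by 0.180 SD for g = 0.8 and by 0.097 SD for g = 0.4.

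- One arm only, g = 0.8: 0.1 × 0.180 = 0.02; 0.3 × 0.180 = 0.05; 0.5 × 0.180 = 0.09 SD.
- Opposite directions, g = 0.8: 0.3 × 0.360 = 0.11; 0.5 × 0.360 = 0.18 SD.
- Opposite directions, g = 0.4: 0.3 × 0.194 = 0.06; 0.5 × 0.194 = 0.10 SD.

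**Step 3: type I error.** With 45 completers per arm and residual variance 1 − 0.5² = 0.75, SE = √(0.75 × 2/45) = 0.183. Type I error = Φ(−1.96 + δ) + Φ(−1.96 − δ), where δ = bias/SE.

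- One arm, b = 0.5: δ = 0.090/0.183 = 0.49, giving about 7.8%.
- Opposite, b = 0.5: δ = 0.180/0.183 = 0.98, giving about 16.6%.

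**Step 4: simulation check** (12,000 trials per row).

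| Drop-out pattern | b | Bias (SD) | Type I, X out | Type I, X in | Check ignoring arm flags X |
|---|---|---|---|---|---|
| One arm, g = 0.8 | 0.1 | 0.02 | 4.9% | 4.8% | 40% |
| One arm, g = 0.8 | 0.3 | 0.05 | 5.9% | 4.9% | 41% |
| One arm, g = 0.8 | 0.5 | 0.09 | 7.9% | 5.1% | 40% |
| Opposite, g = 0.4 | 0.3 | 0.06 | 5.6% | 4.8% | 5% |
| Opposite, g = 0.4 | 0.5 | 0.10 | 8.4% | 5.0% | 5% |
| Opposite, g = 0.8 | 0.3 | 0.11 | 9.1% | 5.0% | 5% |
| Opposite, g = 0.8 | 0.5 | 0.18 | 16.1% | 5.0% | 5% |

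Smaller runs scatter around these values: 6.5% to 8.4% at the upper end of the one-arm case, and up to 17% in the last row. With X in the model, bias is about 0. For b = 0.5 the SE falls from about 0.18 to 0.15; for b = 0.1 it is essentially unchanged.

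**Step 5: where there is no problem.** These cases assume 30% drop-out and g = 1.

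- X affects drop-out equally in both arms: the check flags it in about 99% of trials, but bias is about 0.
- X relates to follow-up only through the baseline score, with opposite directions by arm: bias is about 0 in the model containing that score, but 0.10 SD in the unadjusted t-test.

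**The case against.** Several objections stand and limit the point.

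- **The larger figures need sign reversal.** Nothing in the documents suggests that the same characteristic drives drop-out in opposite directions in two arms. Unequal contact suggests different strength, which is closer to the one-arm case. There the bias is small, and type I error is indistinguishable from 5% at low outcome slopes.
- **A reader might infer that drop-out differing by arm goes unseen.** That holds only for opposite directions. One-arm dependence is flagged about 40% of the time, though not traced to an arm.
- **A reader might infer that controls have no contact for 12 months.** The Control Group section says regular dental care continues; it rules out only further study activities. The raffle (sections 7a and 11) rewards completing assessments in every arm.
- **A reader might infer that the rule always excludes predictors of drop-out.** It does not. Baseline outcome scores can enter as repeated measures, a demographic predictor can enter by chance imbalance, and imputation could include others. But the plan secures none of these routes.
- **That the check pools the arms is itself inferred.** The text is silent on arm. Pooling is the natural reading, and a by-arm intention would need to be stated.
- **The outcome slope is assumed.** The documents give no correlation between demographics and follow-up scores. At slopes of 0.1 to 0.2, even opposite drop-out slopes of 0.8 give only 0.04 to 0.07 SD.

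It is also fair to say that an arm-by-variable test is no cure. In the one-arm case it detects the pattern about as often as the check that ignores arm (58% against 56% at 30% drop-out and g = 1).

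**Conclusion.** The point holds in a limited form. The plan states a covariate rule that selects on baseline difference, and a drop-out check that names no arm and leads nowhere. A collected baseline variable that predicts both drop-out and follow-up will therefore usually be missing from the main model.

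The resulting bias is conditional, not demonstrated. It needs drop-out that depends on the variable differently by arm, and a variable that predicts follow-up beyond the baseline score. With 60 per arm and 25% drop-out it is about 0.02 to 0.09 SD (type I error about 5% to 8%) for one-arm dependence. About 0.18 SD and 17% is an upper figure for an extreme pattern that the documents do not support as likely. They do not show that the trial's result will be biased, since they report neither attrition nor its pattern. The change is worth making because prespecified covariates remove this bias at little cost in precision, and often with a gain.

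**What to change.** 1. **Covariates.** Replace the rule based on differences between groups with a short list, fixed in advance, of collected baseline variables likely to predict outcome or drop-out: for example age, sex, education, income and the baseline scores. Put them in the mixed model, and in any imputation model, whether or not the arms differ on them.
2. **Drop-out reporting.** Give drop-out numbers, and the baseline characteristics of completers and drop-outs, separately by arm. Define a completer as a senior with the primary outcome at one time point common to all arms. The 12- and 18-month statements for Group 2 must be reconciled first.
3. **Do not choose covariates by the observed size of missingness slopes.** With about 15 drop-outs among 60, an unrelated variable shows an absolute log-odds slope above 0.4 in about 19% of arms. Over three arms, 1 − 0.81³ = 0.47, so nearly half of irrelevant variables would qualify in at least one.

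**Cost.** Plan wording only, on data already collected. Age, sex, education and income take 4 degrees of freedom if the last two enter as ordered scores, or 1 + 1 + 5 + 2 = 9 if every category in Appendix C is kept, plus the baseline scores. By-arm drop-out estimates will be imprecise and should be read as description.

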### 1) Abstract of the study

**Introduction:** Older adults have been described as one of the most underserved and vulnerable groups, who are at the highest risk for coronal and root caries, especially because more elderly adults are retaining their teeth. The Northeast Philadelphia KleinLife site is an important destination for the region's Jewish population comprising of at least 6500 seniors, and assisting more than 4500 seniors through food security programs. Recently, Temple University Kornberg School of Dentistry (TUKSoD) purchased the dental center at the facility to expand the services provided to these underserved population and improve their oral health. The study aims to assess the efficacy of an oral health education group based activity versus an individual based oral health education activity in terms of changes in oral health related quality of life (OHRQoL), self-efficacy and oral health knowledge. **Methods:** A sample of 190 senior members will be invited to participate in the trial. Potential subjects will be obtained in person through the ongoing flow of patients at TUKSoD Clinic at Kleinlife and the dental school. Seniors who consent to participate in the study will be randomly allocated to one of the 3 groups (Control: subjects will continue receiving regular dental care at the clinic, Intervention 1: subjects will continue receiving regular dental care at the clinic and be invited to participate in 2 group based education sessions during a 12 month period, and Intervention 2: subjects will continue receiving regular dental care at the clinic and be invited to participate in an individual-based education and prevention activity over a 18 month period. Randomization will be determined according to a predetermined random sequence, and neither the patient nor the research staff will be aware of the randomization outcome until after the patient has agreed to participate. Subjects who consent to participate will be entered into a raffle to receive a \$350-dollar visa gift card, if they complete the baseline and follow up assessments. The OHIP-14 will be used to assess OHRQoL, and self-efficacy scores will be the primary outcomes. Initially, we will assess the differences between the interventions and control using 2-sample *t*-tests. The main analysis will be based on linear mixed-effects models for repeated measures (using the OHIP 14 and self-efficacy scores as continuous outcome variables) to assess differences between intervention and control groups. Similar analyses will be conducted for secondary outcome measures. Statistical significance will be set at  $p < .05$ .

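### Two unranked primary outcomes are each tested at .05 with no rule for a positive trial; if either outcome suffices, the false-positive chance exceeds 5%

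*Combined protocol and SAP*

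**What the plan says.** The Data Analysis section (7d) is the clear source: "OHIP 14 and self-efficacy scores will be the primary outcomes". The Abstract has a looser sentence, "The OHIP-14 will be used to assess OHRQoL, and self-efficacy scores will be the primary outcomes", which read literally attaches the primary label to self-efficacy alone. Neither place orders the two outcomes.

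The analysis has two stages. First, "Initially, we will assess the differences between the interventions and control using 2-sample" t-tests. Then comes a repeated-measures mixed model, which the plan calls its main analysis, used "to assess differences between intervention and control groups". One threshold closes the paragraph: "Statistical significance will be set at" p<.05.

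The Objectives section (4) sets out the comparisons. Its primary objective is group-based against individual education, and it lists oral health knowledge beside the two primary outcomes, although knowledge is also the secondary objective. Its first null hypothesis reads "There are no significant differences in the selected behavioral outcome measures between the interventions, either group-based or individual based education and the control". Its second reads "The two educational interventions are not equivalent in the selected behavioral outcome measures".

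**The concern.** A threshold of .05 per test fixes the error of each test. It does not fix the error of the conclusion that the trial was positive. That depends on how many tests can produce the conclusion and whether one of them is enough, and the plan states neither. Its wording on interventions and control fits a pooled comparison, one test across the three arms, or two separate contrasts, each on two outcomes. The primary objective adds a third contrast.

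At stake is how the result can be read. If one of several tests falls below .05, the plan gives no basis for saying whether the trial met its aim, and the choice could be made after the data are seen.

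**Working it through.** The plan states no familywise error rate, power or sample-size derivation, so there is no figure of its own to reproduce.

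**Inputs from the documents.** Two primary outcomes and a threshold of .05 (Data Analysis). Three arms with 60 seniors each in the trial: control 60, group-based 60, and individual 70 less 10 calibration patients.

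**Assumptions not in the documents.** No true effects, two-sided tests, success on either outcome unless stated otherwise, and outcome correlation 0 to 0.5, with 0.9 as a sensitivity check.

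**Step 1, closed form.** Two independent tests: 1 − 0.95² = 9.75%. Four independent tests: 1 − 0.95⁴ = 18.5%. The second figure is too high here, because both interventions share one control group. With equal arms, the two contrasts on the same outcome correlate at 1/2.

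**Step 2, simulation with the shared control** (normal theory, 4,000,000 draws per setting, |z| > 1.96). Chance of at least one false primary result:

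| What can count as a primary result | Correlation 0 | 0.5 | 0.9 |
|---|---|---|---|
| One test per outcome (2-df arm test, interventions pooled, or one intervention arm only) | 9.7-9.8% | 9.1% | 7.0-7.1% |
| Each intervention against control, both outcomes (4 tests) | 17.3% | 16.1% | 12.6% |
| The same plus group versus individual (6 tests) | 22.9% | 21.3% | 16.7% |
| Both outcomes required in the same intervention arm | 0.5% | 1.8% | 5.5% |

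Simulating t-tests and F-tests with 60 per arm changes the rows checked by about 0.1 percentage point: 16.2% for four tests and 9.2% for the 2-df test at correlation 0.5.

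**Step 3, the remedies under the same assumptions.** With one test per outcome at .025, the rate is 4.9% at correlation 0 and 4.6% at 0.5. With a single primary outcome and one test at .05, it is 5%. Neither remedy alone covers several contrasts. One primary outcome with two intervention-control contrasts at .05 gives 9.1%, and with all three pairwise contrasts 12.2%. If a 2-df arm test must be significant before the pairwise contrasts are examined at the same level, the rate is 5.0% for a single primary outcome and 4.7-4.9% for the split.

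**Step 4, power, for illustration only.** Take a single post-treatment comparison, 60 per arm, true difference 0.516 SD. The expected z is 0.516 × √(60/2) = 2.826.

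- At .05: Φ(2.826 − 1.960) = Φ(0.866) = 0.81; the t distribution gives 0.80.
- At .025: Φ(2.826 − 2.241) = Φ(0.585) = 0.72; the t distribution gives 0.71.
- With the 2-df gate (simulated, the other arm's effect ranging from none to equal): 59-66% at .025 and 70-76% at .05.

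**The case against.** The strongest reply is that the inflation rests on a rule the plan never states. If each outcome is reported as its own claim, each claim tested once keeps a 5% error rate. If both outcomes are required in the same arm, the error is below 2% at correlations up to 0.5. This stands. A reader might infer that the trial carries a 17% or 23% false-positive rate; the documents do not support that as a property of the plan. They show that the success rule is missing, and that the rate exceeds 5% whenever one outcome is enough.

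A second reply is that the plan already favours the mixed model. That also stands: the t-tests come first, but the mixed model is named as the main analysis, so a reader should not infer two rival confirmatory analyses. What remains is small. The same threshold follows both stages, and the t-tests are not called descriptive.

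A third reply is that two distinct interventions sharing a control need no joint error control. Statisticians differ on this, and the point does not depend on it. Within one intervention arm alone, two unranked outcomes give 9-10%.

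In the other direction, even 21-23% is not a ceiling. It leaves out the repeated t-test and mixed-model analyses, the several assessment times, and oral health knowledge.

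**Conclusion.** The concern holds in conditional form. Two primary outcomes stand side by side, each tested at .05, with no statement of which result, or how many, makes the trial positive. If either outcome suffices, the false-positive chance is roughly two to more than four times the nominal 5%, depending on which contrasts count. If both are required in the same arm, there is no inflation at correlations of 0 to 0.5. The arithmetic is secure under the stated assumptions; the outcome correlation, the sidedness and above all the success rule are not in the documents. In a low-risk education trial this is a change that should be made, not a fatal fault.

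**What to change.** In Data Analysis, and to match in the Abstract:

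1. State that the mixed model is the only confirmatory analysis and that the initial t-tests are descriptive.
2. Either name one outcome as the single primary and make the other secondary, or allocate .025 to each.
3. Name the contrasts that count towards success, and say whether group versus individual is confirmatory.
4. Optionally, control error across the interventions too: a 2-df arm test first, then pairwise contrasts at the same level. This is a choice, not a requirement, but the plan should say which way it went.

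The contrasts need a follow-up time assessed in all three arms. For the control arm, "Subjects in this group will complete intake forms to assess main behavioral outcomes, at baseline and after 12 months". The individual arm is described with both a 12-month and an 18-month period, and its forms are given at each visit and after 18 months. The three arm descriptions must be reconciled before the time point is fixed. Pairwise difference tests will not test the equivalence-worded hypothesis in the Objectives.

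The cost is wording only, provided the reconciled schedules leave a common time; adding an assessment would be a design change. In power, on the illustrative 0.52 SD with no drop-out, ranking alone costs the first outcome nothing. Allocating .025 to each lowers power per contrast from about 80% to 71-72%. Adding the gate gives 59-66% with the split, or 70-76% with a single primary outcome. The documents give no effect size or drop-out, so these figures show direction and rough scale, not this trial's actual power.
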